### 6.10.2. Secondary and Tertiary Efficacy Analyses

The LS mean change from baseline to Week 2 in CTT (hours) between galcanezumab 240 mg and erenumab 140 mg will be compared to detect any between-group differences in the primary model described above.

For continuous secondary/tertiary measures with a single postbaseline measurement, analysis will be performed using an ANCOVA model. The analysis will include the categorical effects of treatment and all randomization stratification factors, as well as the continuous baseline value. The LS mean change from baseline in each treatment group will be tested to detect any changes between pre- and post-treatment administration. The LS mean change from baseline in the 2 treatment groups will also be compared to detect any between-group differences.

For continuous efficacy measures with repeated postbaseline measurements, change from baseline will be analyzed using a REML-based MMRM technique. The analysis will include the fixed categorical effects of treatment, pooled investigative site, BMI category ( $<30\text{kg/m}^2$ ,  $\geq 30\text{kg/m}^2$ ), baseline migraine frequency ( $<8$  migraine headache days,  $\geq 8$  migraine headache days), week, and treatment-by-week interaction, as well as the continuous fixed covariates of baseline value and baseline-by-week interaction.

An unstructured covariance structure will be used to model the within-patient errors. The Kenward-Roger (Kenward and Roger 1997) approximation will be used to estimate the denominator degrees of freedom. If the model does not converge, with both the Hessian and the G matrix being positive definite under the default fitting algorithm used by PROC MIXED, the Fisher scoring algorithm will be implemented by specifying the SCORING option in SAS®. If the model still fails to converge, the model will be fit using covariance matrices of the following order specified by a decreasing number of covariance parameters until convergence is met:

- heterogeneous Toeplitz
- heterogeneous first-order autoregressive
- Toeplitz, and
- first-order autoregressive.

When the unstructured covariance matrix is not utilized, the sandwich estimator (Diggle and Kenward 1994) will be used to estimate the standard errors of the fixed-effects parameters. The sandwich estimator is implemented by specifying the EMPIRICAL option in SAS. When the sandwich estimator is utilized, the Kenward-Roger approximation for denominator degrees of freedom (Kenward and Roger 1997) cannot be used. Instead, the denominator degrees of freedom will be partitioned into between-subject and within-subject portions by the DDFM=BETWITHIN option in SAS. SAS PROC MIXED will be used to perform the analysis.

### **6.10.3. Sensitivity Analyses**

The primary analysis assumes that data are normally distributed. To assess the impact of the normality assumption, a nonparametric sensitivity analysis of the primary endpoint will be produced using the Wilcoxon signed rank test (Wilcoxon 1945) to compare the change from baseline within each treatment group.

### **6.10.4. Exploratory Analyses**

If the within-treatment analyses of change from baseline in GET and SBTT are statistically significant for either treatment, the changes in pressure parameters (frequency of contractions, motility index, and AUC) will be assessed for both treatments for the stomach, antrum, duodenum, ileum, caecum, sigmoid, and small bowel (by quartile) using the ANCOVA model described in Section 6.10.2.

Colonic transit time (hours) for patients with treatment-emergent (TE) constipation versus those without TE constipation will be explored. Treatment-emergent constipation is defined as reporting a treatment-emergent adverse event (TEAE) of constipation and/or score of  $\geq 4$  for constipation syndrome from the GSRS assessment. Descriptive statistics and boxplots will be provided by TE constipation category (Yes vs No) for change from baseline in CTT (hours) by treatment separately. Furthermore, if 10 or more patients have TE constipation for each treatment, then ANCOVA analyses will be performed to evaluate the change from baseline in CTT (hours) between TE constipation categories at the end of Week 2 for each treatment. The ANCOVA analyses will include the categorical effects of TE constipation, pooled investigative

site, BMI category ( $<30\text{kg/m}^2$ ,  $\geq 30\text{ kg/m}^2$ ), and baseline migraine frequency ( $<8$  migraine headache days,  $\geq 8$  migraine headache days), as well as the continuous baseline CTT (hours).

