
Secondary Objectives To evaluate transit time of the following segments of the gastrointestinal (GI) tract 1 week prior to and 2 weeks after administration of galcanezumab or erenumab:
 
 • whole gut • gastric emptying • small bowel • combined small and large bowel. 	Change from baseline in GI transit time in each of the following segments after administration of galcanezumab or erenumab within each treatment group at the end of Week 2: 
 • Whole gut transit time (WGTT), in hours • Gastric emptying time (GET), in hours • Small bowel transit time (SBTT), in hours • Combined small and large bowel transit time (SLBTT), in hours.
To evaluate the frequency of contractions, motility index, and area under the pressure curve (AUC) by quartile in the colon to assess for correlation with CTT results.	Changes in pressure parameters from baseline: 
 • Contraction Freq/Min • Motility Index = $\ln(\# \text{ of contractions} \times \sum \text{pressure amplitudes} + 1)$ • Area under the Pressure Curve.
To evaluate number of weekly spontaneous bowel movements (un-aided by laxatives, enemas, or suppositories) prior to and after administration of galcanezumab or erenumab.	Change from baseline in number of weekly spontaneous bowel movements after administration of galcanezumab or erenumab within each treatment group at Weeks 2 and 4.
To evaluate GI symptom rating scale (GSRS) prior to and after administration of galcanezumab or erenumab.	Change from baseline in GSRS after administration of galcanezumab or erenumab within each treatment group at Weeks 2 and 4.
To evaluate the Bristol stool form scale (BSFS) prior to and after administration of galcanezumab or erenumab.	Change from baseline in BSFS after administration of galcanezumab or erenumab within each treatment group at Weeks 2 and 4.

Tertiary/Exploratory Objectives To evaluate the transit time between galcanezumab and erenumab for
 
 • whole gut • gastric emptying • small bowel • colon • combined small and large bowel. 	Change from baseline in transit time after administration of galcanezumab or erenumab between treatment groups at the end of Week 2 for 
 • WGTT, in hours • GET, in hours • SBTT, in hours • CTT, in hours • combined SLBTT, in hours.

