**Table CGBC.4.1. Secondary and Tertiary Objectives and Endpoints**

Objectives	Endpoints

Secondary Objectives
 
To evaluate transit time of the following segments of the gastrointestinal (GI) tract 1 week prior to and 2 weeks after administration of galcanezumab or erenumab:
 
 
• whole gut
 
• gastric emptying
 
• small intestine, and
 
• combined small and large bowel.
 
	
Change from baseline in GI transit time in each of the following segments after administration of galcanezumab or erenumab within each treatment group at the end of Week 2:
 
 
• whole gut transit time (WGTT), in hours
 
• gastric emptying time (GET), in hours
 
• small intestine bowel transit time (SBTT), in hours, and
 
• combined small and large bowel transit time (SLBTT), in hours.
 

To evaluate the frequency of contractions, motility index, and area under the pressure curve (AUC) by quartile in the colon to assess for correlation with colonic transit time (CTT) results.
	
Changes in pressure parameters from baseline:
 
 
• contraction freq/min
 
• motility index = <math>\ln(\# \text{ of contractions} \times \sum \text{pressure amplitudes} + 1)</math>, and
 
• Area under the pressure curve (AUC).
 

To evaluate number of weekly spontaneous bowel movements (un-aided by laxatives, enemas, or suppositories) prior to and after administration of galcanezumab or erenumab.
	
Change from baseline in number of weekly spontaneous bowel movements after administration of galcanezumab or erenumab within each treatment group at Weeks 2 and 4 post-treatment.

To evaluate GI symptom rating scale (GSRS) prior to and after administration of galcanezumab or erenumab.
	
Change from baseline in GSRS after administration of galcanezumab or erenumab within each treatment group at Weeks 2 and 4 post-treatment.

To evaluate the Bristol Stool Form Scale (BSFS) prior to and after administration of galcanezumab or erenumab.
	
Change from baseline in BSFS after administration of galcanezumab or erenumab within each treatment group at Weeks 2 and 4 post-treatment.

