### 5.4. Measures

#### 5.4.1. Primary Measures

The SmartPill™ WMC technology (Medtronic, Minneapolis, MN, USA) will be used to evaluate total gastrointestinal (GI) transit time and segmental transit time. The WMC measures whole gut and regional gut (stomach, small bowel, and colon) transit times through measurement of pH, pressure, and temperature throughout the GI tract. Once enrolled in the study, patients will be asked to eat a SmartBar, followed by ingesting the WMC with 120 mL of water. Patients will be instructed to fast for an additional 6 hours after ingesting the WMC and to wear an external data recorder for up to 5 days. The WMC is a 4.5-g indigestible, single-use,  $27 \times 12$  mm cylindrical capsule. Data will be transferred to the wearable external data recorder and displayed and analyzed using Medtronic MotiliGI™ version 3.1 software (Medtronic, Minneapolis, MN, USA).

The baseline and postbaseline WMC tests will be assessed by expert readers who are blind to treatment assignment.

The primary outcome measure is CTT in hours. Secondary transit time outcome measures include the whole gut transit time in hours, gastric emptying time (GET) in hours, small intestine bowel transit time (SBTT) in hours, and small and large bowel transit time (SLBTT) in hours. All transit time outcome measures will be collected at baseline and 2 weeks after study drug administration.

Further secondary outcome measures include contraction, measured as frequency per minute, motility index, and AUC.

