### 6.5. Multiple Comparisons/Multiplicity

All tests of within-group and between-group comparisons will be conducted at a 2-sided alpha level of 0.05, unless otherwise stated.

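### SAP 6.10.4 triggers the caecum and sigmoid pressure analyses on gastric and small-bowel transit instead of CTT, and the colon-pressure correlation with CTT named in a secondary objective has no analysis

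*SAP*

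**What the plan says.** SAP 6.10.4 opens with a condition: "If the within-treatment analyses of change from baseline in GET and SBTT are statistically significant for either treatment". When it is met, changes in contraction frequency, motility index and AUC are assessed in both treatments "for the stomach, antrum, duodenum, ileum, caecum, sigmoid, and small bowel (by quartile) using the ANCOVA model described in Section 6.10.2". CTT is not part of the condition.

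Separately, Table CGBC.4.1 in the SAP and Table CGBC.4.1 in Protocol Section 4 make colonic pressure a secondary objective. The SAP wording is "by quartile in the colon to assess for correlation with colonic transit time (CTT) results"; the protocol wording is "by quartile in the colon to assess for correlation with CTT results". The paired endpoint is change from baseline in the three pressure parameters.

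SAP 5.4.1 confirms their status: "Further secondary outcome measures include contraction, measured as frequency per minute, motility index, and AUC". SAP 6.10.2 covers such measures with no precondition: "For continuous secondary/tertiary measures with a single postbaseline measurement, analysis will be performed using an ANCOVA model". The test level comes from SAP 6.5: "All tests of within-group and between-group comparisons will be conducted at a 2-sided alpha level of 0.05, unless otherwise stated".

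Neither Protocol 10.3.3 nor SAP 6.10 specifies a correlation coefficient, regression or other method relating colon pressure to CTT.

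**The concern.** There are two linked gaps.

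**The trigger.** Two of the seven conditional regions, caecum and sigmoid, are colonic, but the condition looks only at stomach and small-bowel transit. The study was designed to explore a mechanism behind constipation (Protocol 3.1 and 3.2), and the primary endpoint is CTT. The pattern in which one would most want to know where in the colon motility changed is slower colonic transit with unchanged GET and SBTT. In that pattern the plan does not call for the caecum and sigmoid analyses.

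**The correlation.** The secondary objective gives correlation with CTT as the purpose of measuring colonic pressure. ANCOVA of mean change shows whether average pressure moved in an arm. It cannot show whether the patients whose pressure changed are the ones whose CTT changed. With no method named, the choice of coefficient, pooling and segment would be made after the data are seen, in a study where the sponsor knows treatment throughout (SAP 6.12).

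The wording of the condition is also open to more than one reading. *GET and SBTT* may mean both or either, and the text does not say whether two significant results must come from the same arm. Two programmers could produce different outputs.

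**Working it through.** **The plan's own figure.** SAP 5.2 and Protocol 10.1 give a mean CTT change of 4.2 h, SD 8, 30 patients per arm and 80% power. The standardised change is 4.2/8 = 0.525. A two-sided one-sample t-test at 0.05 with n = 30 has power 79.4%; the normal approximation gives 82.0%. The 80% reproduces. It applies to CTT only. The documents give no power for GET, SBTT or any pressure parameter, so it is not used below.

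**Chance that the condition is met when only the colon changes.** Inputs: two-sided level 0.05 (SAP 6.5), no true change in GET or SBTT, and two arms treated as independent. The documents give no correlation between the GET and SBTT tests, so the range 0 to 1 is an assumption.

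| Reading of the condition | Per-arm probability | Condition met |
|---|---|---|
| Both, same arm, independent | 0.05² = 0.0025 | 1 − (1 − 0.0025)² = 0.5% |
| Both, same arm, correlation 0.5 (simulated) | 0.0093 | 1.8% |
| Both, same arm, correlation 0.7 (simulated) | 0.0165 | 3.3% |
| Both, same arm, correlation 1 | 0.05 | 1 − 0.95² = 9.75% |
| Both, possibly from different arms, independent | not per arm | (1 − 0.95²)² = 0.95% |
| Either, independent | 1 − 0.95² = 0.0975 | 1 − (1 − 0.0975)² = 18.5% |
| Either, correlation 1 | 0.05 | 9.75% |

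On every reading, the condition is met only through a false-positive upper-gut test.

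**A change confined to the stomach.** If both tests must be significant in the same arm and SBTT does not truly change, the probability in that arm cannot exceed 0.05, the level of the SBTT test, however strong the GET effect. The same holds with the roles reversed. On this reading, a real single-segment change would usually leave its own segment unexamined.

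**What is analysed regardless.** The conditional list reads "for the stomach, antrum, duodenum, ileum, caecum, sigmoid, and small bowel (by quartile"). It includes neither the colon as a whole nor its quartiles. Those fall under the secondary objective, are secondary measures under SAP 5.4.1, and are covered by the unconditional ANCOVA in SAP 6.10.2. The condition therefore removes only the additional regions.

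**Precision of the missing correlation.** By the Pearson Fisher-z approximation at r = 0 with complete data, the 95% half-width is tanh(1.96/√(n − 3)). For n = 30 this is tanh(1.96/√27) = 0.36; for n = 60 it is tanh(1.96/√57) = 0.25. For a Spearman coefficient these values are a guide only.

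**The case against.** The strongest reply is that the colon is not neglected. Colon pressure by quartile is analysed within and between arms with no condition, and the endpoint named for that objective, change in the pressure parameters, is delivered. SAP 6.10.4 also describes CTT change by treatment-emergent constipation without reference to GET or SBTT, and Protocol 10.3.1 allows further exploratory analyses, so nothing forbids caecum and sigmoid tables after a CTT finding. This stands in large part. A reader might infer that a colon-only effect would go unexplained or that colonic pressure analysis is switched off. The documents do not support that.

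It is also fair that requiring both tests is only one reading of the sentence, and that 0.5% needs that reading together with independence of two tests made on the same patients. For that reason the result is given as a range.

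A reader might also call the rule too strict even when GET and SBTT truly change: with an assumed 80% power for each test and independence, it opens in a given arm 0.8² = 64% of the time. The documents give no such power. Moreover, significance in either arm opens the analyses for both, so with both arms affected and the same assumptions the figure is 1 − (1 − 0.64)² = 87%. I place no weight on the 64%.

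The reply does not remove two facts. The caecum and sigmoid analyses have a stated trigger that ignores the primary endpoint. And permission for additional exploratory work is not a prespecified analysis of a relationship that a secondary objective names.

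**Conclusion.** The point holds in a limited form. Under a colon-only effect, the caecum and sigmoid pressure analyses would run only by chance: 0.5% if both tests must be significant in the same arm and are independent, up to 9.75% under assumed positive correlation, and 18.5% if either test suffices and they are independent. The loss is caecum and sigmoid localisation; the colon quartile analysis is unaffected.

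The missing correlation is the firmer of the two gaps, because it serves a secondary objective and does not depend on how the condition is read. It would be too strong to say that the objective is wholly unanswered: its endpoint is analysed, while the patient-level link to CTT is not.

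The matter is minor. The conditional analyses are exploratory and the primary analysis is untouched. The figures assume no true change in GET or SBTT, independent arms and, where stated, a correlation that the documents do not give.

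**What to change.** 1. In SAP 6.10.4, take caecum and sigmoid out of the GET/SBTT condition. Report them with the colon quartiles, or trigger them on the CTT result.
2. State the remaining condition by segment: stomach and antrum on GET; duodenum, ileum and small bowel on SBTT. Say explicitly that significance in one arm suffices, if that is the intent.
3. In SAP 6.10.2, prespecify Spearman correlations of change in each colonic pressure parameter, by quartile, with change in CTT. Report them by arm with 95% confidence intervals and label them nominal. Adjust any pooled estimate for treatment, because a difference between arms in both measures can by itself create a correlation.

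The cost is a few SAP lines and extra tables from data that the capsule already records. The downside is more exploratory output with wide intervals, about ±0.36 around zero in an arm of 30, which is a reason to show the intervals and not rely on p-values.

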WMC administration		X ^a		X		
 • Fasting is defined as no food or drink, except water, for at least 8 hours prior to testing. • No alcohol consumption for 24 hours prior to ingesting the WMC and 6 hours after ingestion. • Tobacco use should also be avoided for 8 hours before ingestion and 6 hours after ingestion of the WMC. • Patients will consume a SmartBar immediately before ingesting WMC and will fast for 6 hours following WMC ingestion. • Patients should not sleep for 6 hours after ingesting the WMC.
Assessment that WMC has been expelled			X ^b	X ^b		The recorder will be returned to the site and data will be uploaded and evaluated to confirm WMC expulsion at Visit 3 and between Visits 4 and 5.
Study treatment administered			X			
Procedures						
Informed consent	X					
Inclusion and exclusion criteria	X					
Concomitant medication review	X	X	X	X	X	

Study Period	SP I Screening and Baseline GI Transit Time		SP II Single-Blind Treatment and Post WMC Evaluation			Notes
	V1	V2	V3	V4	V5	
Urine pregnancy test, performed locally	X				X	
Eligible patient randomized via IWRS			X			
Physical examination	X					
Height	X					
Weight	X					
Medical history	X					
Substance use	X		X	X		Substances: alcohol, caffeine, nicotine, tobacco.
Vital signs	X		X	X	X	Includes body temperature, sitting blood pressure, and pulse.
Assessment of migraine and headache days	X					Will be done retrospectively for the previous month.
GI Symptom Rating Scale (GSRS)	X		X	X	X	
Bristol Stool Form Scale	X		X	X	X	
Spontaneous Bowel movement (SBM) frequency evaluation	X		X	X	X	
Adverse events	X	X	X	X	X	

Abbreviations: GI = gastrointestinal; IBS = irritable bowel syndrome; IWRS = interactive web-response system; SP = study period; TT = transit time; V = visit; WMC = wireless motility capsule.

- ^a If the patient meets the requirement of fasting at Visit 1, then Visit 1 and Visit 2 could be combined. Sites must not instruct patients to fast prior to signing the ICF
- ^b An x-ray may be obtained in the event that the expulsion of the WMC cannot be confirmed.

3. Introduction

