6.2. Exclusion Criteria

Patients will be excluded from study enrollment if they meet any of the following criteria at screening:

Medical Conditions

- [12] Prior to Visit 1, less than 3 bowel movements in the previous 7 days.
- [13] Patients with a history of irritable bowel syndrome (IBS) or chronic constipation.
- [14] Patients with a self-reported history of gastric bezoars, swallowing disorders, severe dysphagia to food or pills, suspected or known strictures, fistulas, or physiological/mechanical GI obstruction.
- [15] History of GI surgery with the exception of cholecystectomy, appendectomy, or Nissen fundoplication.
- [16] History of any abdominal surgery within the past 3 months.
- [17] History of bariatric surgery.
- [18] History of Crohn's disease, celiac disease, ulcerative colitis, or diverticulitis.
- [19] Patients with type 1 or type 2 diabetes.
- [20] Patients with cardiac pacemakers or other implanted or portable electromechanical device.
- [21] Patients with a body mass index (BMI) of ≥ 40 kg/m².
- [22] Women who are pregnant or nursing.
- [23] History of drug or alcohol abuse/dependence within 1 year prior to Visit 1 (excessive or compulsive use as judged by the investigator), or currently using drugs of abuse (including opioids, barbiturates, and marijuana), or any prescribed or over-the-counter medication in a manner that the investigator considers indicative of abuse/dependence.

- [24] Have an acute, serious, or unstable medical condition that, in the judgment of the investigator, indicates a medical problem that would preclude study participation.
- [25] Myocardial infarction, unstable angina, percutaneous coronary intervention, coronary artery bypass graft, stroke, deep vein thrombosis, or pulmonary embolism within 6 months of screening, or have planned cardiovascular surgery or percutaneous coronary angioplasty.
- [26] Patients who, in the clinician's judgment, are actively suicidal and therefore deemed to be at significant risk for suicide, or have had clinically significant suicidal ideation within the past month (e.g., includes some plan or intent to act), or have had any suicidal behavior within the past month.

Prior/Concomitant Therapy

- [27] Patients currently receiving a mAb CGRP antagonist or have received a mAb CGRP antagonist within the past 6 months prior to Visit 1.
- [28] Have received an oral CGRP antagonist (gepant) 14 days prior to Visit 1.

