#### 5.4.2. Other Secondary Measures

**Gastrointestinal Symptom Rating Scale:** The Gastrointestinal Symptom Rating Scale (GSRS) is a validated 15-item questionnaire that evaluates the 5 common symptoms of GI disorders: abdominal pain, reflux, indigestion, constipation, and diarrhea. Items contain questions about

the past week using a 7-point categorical response scale ranging from no discomfort to very severe discomfort (Revicki et. al 1998; Khanna et al. 2017). Based on a factor analysis, the 15 GSRS items are summarized by the 5 scales, which are calculated by taking the mean of the items completed within an individual scale. The GSRS is grouped accordingly by

- abdominal pain – abdominal pain, hunger pains, and nausea
- reflux syndrome – heartburn and acid reflux
- diarrhea syndrome – diarrhea, loose stools, and urgent need to have a bowel movement
- indigestion syndrome – rumbling, bloating, belching, and increased flatus (breaking wind); and
- constipation syndrome – constipation, hard stools, and sensation of not completely emptying the bowels.

**Bristol Stool Form Scale:** The Bristol Stool Form Scale (BSFS) is 7-point ordinal scale of stool types ranging from the hardest (type 1) to the softest (type 7). Symptoms of constipation are related to harder stools (types 1 and 2), and symptoms of diarrhea are related to loose/liquid stools (types 6 and 7). Overall, stool types 3 to 5 are considered normal. The BSFS provides the patient with a pictorial representation of each type of stool (Blake et al. 2016).

**Spontaneous Bowel Movement Frequency Evaluation:** The spontaneous bowel movement (SBM) frequency evaluation is the number of spontaneous (nonintervention induced) bowel movements that a patient has had in the past 7 days. Patients are asked how many SBMs they have had in the past 7 days, and the information is collected on the case report form (CRF) for Visits 1, 3, 4, and 5.

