### 6.11.1. Extent of Exposure

Patients will receive study treatment at the beginning of Visit 3.

The following information will be recorded on the eCRF for each dose:

- confirmation that the patient received study treatment (including reason if study treatment was not administered), and
- date and time of administration.

A listing of patient exposure will be produced.

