### **6.11.3. Adverse Events**

Treatment-emergent AEs are defined as reported AEs that first occurred or worsened during the postbaseline phase compared with the baseline phase. For each TEAE, severity (mild, moderate, or severe) will be determined by patient or physician opinion. The Medical Dictionary for Regulatory Activities (MedDRA) lowest level term (LLT) will be used in the TE computation. For each LLT, the maximum severity at baseline will be used as the baseline severity. If the maximum postbaseline severity is greater than the maximum baseline severity, the event will be considered TE for the specific postbaseline period.

For each patient and TEAE, the maximum severity for the specified MedDRA level (PT, high level term, or SOC) will be the maximum postbaseline severity observed from all associated LLTs mapping to that MedDRA level.

For events that are gender specific, the denominator and computation of the percentage will include only patients from the specified gender.

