#### **6.11.6. Vital Signs and Other Physical Findings**

Vital signs collected during the study include systolic (SBP) and diastolic blood pressure (DBP), pulse, and temperature. Blood pressure and pulse measurements will be taken when the patient is in a sitting position.

The number and percent of patients meeting criteria for categorical changes of interest in vital signs at any time during study will be summarized. Treatment group comparisons will be performed using Fisher's exact test.

[Table CGBC.6.1](#) displays the criteria for categorical changes of interest in vital signs. The last column of the table displays the patient populations defined by baseline categories.

The criteria to identify patients with TE abnormal changes generally consist of 2 parts: an absolute threshold and a change from baseline amount.

- The absolute threshold in the criteria is based on 1) minimum postbaseline when the direction is low; 2) maximum postbaseline when the direction is high.
- The change from baseline amount in the criteria is 1) decrease from baseline to minimum postbaseline when the direction is low, and 2) increase from baseline to maximum postbaseline when the direction is high.

The baseline for SBP, DBP, pulse, and temperature is defined as the last non-missing baseline value during the baseline period. This baseline definition for SBP, DBP, pulse, and temperature applies to all analyses (both continuous and categorical) for SBP, DBP, pulse, and temperature.

Any clinically significant finding from vital sign measurements that results in a diagnosis and that occurs after the patient receives the first dose of study treatment should be reported as an AE via eCRF to Eli Lilly and Company or its designee.

Other physical findings will be collected at Visit 1. No analyses of other physical findings will be produced.

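### SAP 6.10.4 counts an unchanged GSRS constipation score of 4 or more as treatment-emergent, because the GSRS part of the definition has no baseline condition and names no visit

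*SAP*

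**What the plan says.** SAP 6.10.4 plans to compare change from baseline in CTT between patients with and without treatment-emergent constipation, separately by treatment. The grouping rule is: "Treatment-emergent constipation is defined as reporting a treatment-emergent adverse event (TEAE) of constipation and/or score of" 4 or more on the GSRS constipation syndrome scale. Descriptive statistics and boxplots are always produced. An ANCOVA follows only if at least 10 patients in each treatment are classed as Yes.

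The constipation scale has three items on 7-point responses, asked about the past week, and the score is "calculated by taking the mean of the items completed within an individual scale" (SAP 5.4.2). The Protocol's Schedule of Activities collects GSRS at Visits 1, 3, 4 and 5, so scores exist before and after dosing.

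Elsewhere the SAP ties the term to a comparison with baseline. For adverse events (SAP 6.11.3): "Treatment-emergent AEs are defined as reported AEs that first occurred or worsened during the postbaseline phase compared with the baseline phase". For vital signs (SAP 6.11.6): "The criteria to identify patients with TE abnormal changes generally consist of 2 parts: an absolute threshold and a change from baseline amount".

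**The concern.** The two parts of one definition carry different meanings. A patient who enters through the adverse-event part must have something new or worse after dosing. A patient who enters through the GSRS part needs only a score at or above the cut-off, whatever it was beforehand. Someone with steady symptoms throughout is therefore placed in the group meant to hold new or worsened constipation.

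The aim of the analysis is to see whether symptomatic constipation after dosing goes with a change in colonic transit. Patients whose symptoms did not change blur that contrast, and they can help to trigger the ANCOVA.

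The missing visit matters as well. The phrase about the end of Week 2 in SAP 6.10.4 dates the CTT change, not the GSRS score. A patient who first reaches 4 at Visit 5 could be classed either way, and two programmers could build different groups from the same data.

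**Working it through.** The plan gives no figure on this point to reproduce, and the sample-size figures do not enter. The check applies the rule to example scores and then works out the consequence.

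**1. Classification.** Inputs: three items, score equal to their mean, cut-off 4 (SAP 5.4.2 and 6.10.4). With all items answered, a score of 4 or more needs an item sum of at least 12, and the smallest possible rise is 1/3. Assume that the patient reports no constipation TEAE.

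| Items before → after | Score before → after | SAP rule, postbaseline scores only | 4 or more and above baseline |
|---|---|---|---|
| 4,4,4 → 4,4,4 | 4.0 → 4.0 | Yes | No |
| 5,5,4 → 4,4,4 | 4.67 → 4.0 | Yes | No |
| 2,2,2 → 4,4,4 | 2.0 → 4.0 | Yes | Yes |
| 5,5,5 → 2,2,2 | 5.0 → 2.0 | No | No |

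The first two rows are the problem: no worsening, yet classed as treatment-emergent.

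**2. Effect on the unadjusted contrast.** Let D be the true Yes-No difference in mean CTT change, m the number labelled Yes, and k those among them who were at 4 or more before dosing, stayed there without worsening and had no constipation TEAE. Assume that these k have the No group's mean change. Then

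observed difference = [(m - k) × D + k × 0] / m = (1 - k/m) × D.

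| m | k = 0 | k = 1 | k = 2 | k = 3 |
|---|---|---|---|---|
| 10 | 1.0 | 0.9 | 0.8 | 0.7 |
| 5 | 1.0 | 0.8 | 0.6 | 0.4 |

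The values of k are assumptions; the documents give none.

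**3. The trigger.** An arm with 10 Yes patients, 1 of them unchanged, has 10 - 1 = 9 new or worsened cases, below the threshold. This matters only if the other arm also reaches 10.

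As an illustration, take 30 patients per arm (SAP 5.2) and assume a true treatment-emergent rate of 20%. Let b be the assumed share of the remaining patients who are at 4 or more before dosing and stay there without worsening. The labelled rate is 0.20 + 0.80 × b, and the expected number misclassed per arm is 30 × 0.80 × b. The last column assumes the same rate in both arms and independence.

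| b | Labelled rate | Misclassed per arm | Share truly emergent | P(10 or more), one arm | P(10 or more), both arms |
|---|---|---|---|---|---|
| 0 | 0.200 | 0 | 100% | 6% | 0.4% |
| 2% | 0.216 | 0.5 | 93% | 9% | 0.9% |
| 5% | 0.240 | 1.2 | 83% | 16% | 2.6% |
| 10% | 0.280 | 2.4 | 71% | 32% | 10% |

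With a true rate of 10%, the chance that both arms reach 10 is at most 0.2% over this range of b. With a true rate of 30%, it rises from 17% to 52%.

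**The case against.** The strongest objection is that the situation may hardly arise. Protocol 6.2 excludes "Patients with a history of irritable bowel syndrome (IBS) or chronic constipation", fewer than 3 bowel movements in the 7 days before Visit 1, and drugs known to alter GI transit. A mean of 4 across three items is a substantial score in such a population. This stands as a limit on size. It does not remove the point, because no GSRS limit is set at entry and a stool count does not measure hard stools or incomplete emptying.

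It can also be said that the label itself implies postbaseline scores. That is the sensible reading, but it adds a time window and no worsening condition. The safety definitions of baseline and postbaseline in SAP 6.11 add none either.

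A reader might go further and infer that a high pre-dose score alone makes a patient treatment-emergent, so that 5.0 falling to 2.0 would be Yes. The documents do not support this. The SAP links the term to the postbaseline phase for adverse events and to postbaseline extremes for vital signs. Nor do those two sections govern GSRS; they show only how the SAP uses the term elsewhere.

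Two further limits stand. The factor (1 - k/m) describes the unadjusted contrast, not an ANCOVA that adjusts for baseline CTT, pooled site, BMI category and migraine frequency. And since 10 patients are needed in each treatment, while Protocol 3.2 expects little or no change in transit with the ligand antibody, the analysis may well stay descriptive.

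**Conclusion.** The definition misclassifies patients who are at 4 or more before dosing and remain there without worsening. This follows from the wording and depends on no assumed rate. How many such patients there will be is not in the documents; the number is probably small and may be 0.

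If they share the No group's mean change, the unadjusted difference shrinks by the fraction k/m. If their CTT change differs from that mean, the bias can be smaller or run the other way. Its size and direction in the ANCOVA are unknown.

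A reader might infer that the trial's main results are at risk. They are not: the primary CTT analysis, the secondary analyses (including "Change from baseline in GSRS after administration of galcanezumab or erenumab within each treatment group at Weeks 2 and 4 post-treatment") and the safety analyses do not use this grouping. Severity is minor.

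**What to change.** In SAP 6.10.4, define the GSRS part as a constipation syndrome score of 4 or more at named postbaseline visits (Visit 4, Visit 5 or either) that is also higher than the patient's baseline score. In choosing the visits, note that a Visit 5 score describes a week well after the second capsule was swallowed.

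State the baseline in the same place, because the SAP does not say which visit supplies the GSRS baseline. Use the last GSRS completed before injection: Visit 3 if completed before dosing, otherwise Visit 1. The order matters because SAP 6.11.1 says: "Patients will receive study treatment at the beginning of Visit 3". A form completed after injection at that visit should be neither baseline nor postbaseline, since its one-week recall is almost wholly pre-dose.

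Requiring any rise would still admit 4.00 to 4.33, one item moving one point. Whether to require a larger rise, or a baseline below 4, is a choice to be written down before the data are analysed.

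The cost is one or two sentences and no new data. The Yes group becomes smaller, so the ANCOVA is less likely to run. Patients with unchanged symptoms move to the No group, which then means not newly or more constipated, rather than free of symptoms.
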